7.8. Concomitant Therapy

All asthma medications used within approximately 6 weeks prior to screening and during the study (including the post-treatment period) should be recorded in the eCRF.

All non-asthma medications taken during the study (after randomization including post-treatment) and any changes to concomitant medications will be recorded in the eCRF.

Note: Study provided FF 100 mcg and albuterol/salbutamol should not be recorded in the eCRF; however non-study supplied FF 100 mcg and albuterol/salbutamol will be recorded in the eCRF.

The minimum requirement is that the drug name, reason for use, dose (including unit e.g. mcg) and frequency, route and the dates of administration are to be recorded.

Medications initiated after completion of the assessments at Visit 5/EOS or the Early Withdrawal Visit will not be recorded in the eCRF unless taken to treat an AE or asthma exacerbation. Detailed information of permitted and prohibited medications is included in the SRM for your reference. Participants who have completed the Early Withdrawal Visit are allowed to use any medications prescribed by the Investigator or primary care physician.

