This is a Phase IIb, randomized, double-blind, placebo controlled, 3-arm parallel group study, comparing the efficacy, safety and tolerability of UMEC (62.5 mcg and 31.25 mcg) administered once-daily in participants with asthma that is not well controlled (i.e. participants with an Asthma Control Questionnaire-6 [ACQ-6] total score >0.75 at Visit 2 [the Randomization Visit]) despite treatment with maintenance ICS.

205832 Study – UMEC (62.5 mcg) vs UMEC (31.25 mcg) vs Placebo

Number of Participants:

The total number of randomized participants required is approximately 384, with 128 participants randomized 1:1:1 to each of the 3 double-blind treatment arms.

Treatment Groups and Duration:

Eligible participants will be requested to participate in the study for a maximum of approximately 31 weeks (Visit 0 to the Follow-up contact, inclusive) during which time, participants will complete the following 4 phases of the study:

- **Pre-screening:** Details about the study and procedures will be explained through the informed consent process. The Pre-screening Visit (Visit 0), including the informed consent process, must be completed within 4 weeks prior to Visit 1 as well as prior to any protocol-required changes to a participant's usual asthma treatment and the initiation of any Visit 1 procedures.
Participants that receive LABA (or LAMA) as a component of their regular (i.e. pre-study) therapy must stop LABA (or LAMA) treatment from ≥ 48 hours prior to Visit 1 (Screening) until after they have completed the study; therefore, the investigator must use their clinical judgment to determine if the participant may stop LABA (or LAMA) prior to study entry without incurring undue risk.

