5. STUDY DESIGN

5.1. Overall Design

This is a Phase IIb, randomized, double-blind, placebo controlled, 3-arm parallel group study, comparing the efficacy, safety and tolerability of UMEC (62.5 mcg and 31.25 mcg) administered once-daily in participants with asthma that is not well controlled (i.e. participants with an ACQ-6 total score >0.75 at Visit 2 [the Randomization Visit]) despite treatment with maintenance ICS.

205832 Study – UMEC (62.5 mcg) vs UMEC (31.25 mcg) vs Placebo

Eligible participants will be requested to participate in the study for a maximum of approximately 31 weeks (Visit 0 to the Follow-up contact, inclusive) during which time, participants will complete the following 4 phases of the study:

- **Pre-screening:** Details about the study and procedures will be explained through the informed consent process. The Pre-screening Visit (Visit 0), including the informed consent process, must be completed within 4 weeks prior to Visit 1 as well as prior to any protocol-required changes to a participant's usual asthma treatment and the initiation of any Visit 1 procedures. Subjects will continue treatment with their regular (i.e. pre-study) asthma medication(s) during the pre-screening period; however, medications that are prohibited within a specified time interval prior to Visit 1 are defined in Section 7.9.

Participants that receive LABA (or LAMA) as a component of their regular (i.e. pre-study) therapy must stop LABA (or LAMA) treatment from ≥ 48 hours prior to Visit 1 (Screening) until they have completed the study; therefore, the investigator must use their clinical judgment to determine if the participant may stop LABA (or LAMA) prior to study entry without incurring undue risk.

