- **Screening / run-in:** Participants who meet all the eligibility criteria at Visit 1 (Screening), will enter the run-in period for approximately 2 weeks to continue assessing the participant's eligibility for the study. On the morning of Visit 1, participants will refrain from taking the morning dose of their regular (i.e. pre-study) ICS asthma medication. Participants satisfying all inclusion/exclusion criteria and who have successfully completed all protocol procedures at screening will be provided with FF 100 mcg via the ELLIPTA dry-powder inhaler (DPI) to take once daily (QD), in the morning, during the 2-week run-in period; the first dose of FF 100 mcg will be self-administered by the participant before leaving the clinic. Participants will refrain from using their own ICS asthma medication during the 2-week run-in and treatment period. Participants will also be provided with rescue medication (albuterol/salbutamol) to use on an as-needed basis throughout the study.
- **Randomization / treatment:** At Visit 2 (the Randomization Visit), participants who meet all of the randomization criteria will be randomized 1:1:1 to receive **one** of the following three double-blind study treatments via the ELLIPTA DPI during the 24-week treatment period:

- UMEC 62.5 mcg QD
- UMEC 31.25 mcg QD
- Placebo QD

Participants will continue to administer FF 100 mcg once daily (QD), in the morning from a separate ELLIPTA DPI throughout the treatment period. On the morning of Visits 2, 3, 4, and 5, participants will perform their electronic Diary (eDiary) assessments at home but refrain from taking their morning dose of study treatment and FF 100 mcg (as applicable) until instructed to do so by clinic personnel. At Visits 2, 3, 4 and 5, participants will self-administer study treatment immediately followed by FF 100 mcg whilst at the clinic (see Section 7.2). Participants will take their last dose of study treatment and FF 100 mcg in the clinic on Day 169 (Visit 5). Participants are expected on non-clinic visit days to take their study treatment and FF 100 mcg at home in the morning at approximately the same time each day, as directed by the clinic.

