7.9. Prohibited Medications and Non-Drug Therapies

Use of the medications listed in [Table 3](#) is not permitted during the study.

Table 3 Concomitant Medications

Medication	No use during the study and/or within the following time interval before Visit 1
Inhaled short-acting anticholinergics	6 hours
Inhaled short-acting anticholinergics+ Short-acting beta agonist combination	6 hours
Inhaled long-acting anticholinergics other than study treatment	2 days
Immunosuppressive medications including immunomodulators	12 weeks
Inhaled long-acting beta ₂ -agonists (e.g., salmeterol, formoterol) or combination products containing inhaled long-acting beta ₂ -agonists (e.g., Seretide, Symbicort)	2 days 10 days prior to Visit 1 for Indacaterol and Olodaterol component.
Inhaled very long-acting beta ₂ -agonists, (Indacaterol, Olodaterol) Oral long-acting beta ₂ -agonists (e.g., bambuterol)	
Inhaled short-acting beta ₂ -agonist (rescue albuterol/salbutamol will be provided and is permitted during the study)	6 hours (including all study visits)

Theophyllines, slow-release bronchodilators, ketotifen, nedocromil sodium, sodium cromoglycate, roflumilast	48 hours Temporary use will be permitted during the study to treat moderate asthma exacerbations
Anti-leukotrienes	48 hours. Temporary use will be permitted during the study to treat moderate asthma exacerbations
Any other investigational drug	30 days or within 5 drug half-lives of the investigational drug (whichever is longer)

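### The bar on maintenance LABA/LAMA and sustained use of other Table 3 asthma controllers does not lift when a participant permanently stops double-blind treatment but stays in the study, which is a safety concern and may discourage retention

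*Protocol*

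**What the plan says.** **The general bar.** Section 7.9 opens: "Use of the medications listed in [Table 3](#) is not permitted during the study". The table includes inhaled LABAs, "Inhaled long-acting anticholinergics other than study treatment", anti-leukotrienes, and a group with theophyllines and similar agents. For the last two rows it adds an exception: "Temporary use will be permitted during the study to treat moderate asthma exacerbations". Section 7.8.1.1 likewise allows temporary changes to treat moderate exacerbations.

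**The separate LABA/LAMA rule.** Section 5.1 states: "Participants that receive LABA (or LAMA) as a component of their regular (i.e. pre-study) therapy must stop LABA (or LAMA) treatment". The stop runs from at least 48 hours "prior to Visit 1 (Screening) until they have completed the study". The synopsis has the same rule, ending "prior to Visit 1 (Screening) until after they have completed the study".

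**The release.** Section 7.8 has one sentence that lifts restrictions generally before completion: "Participants who have completed the Early Withdrawal Visit are allowed to use any medications prescribed by the Investigator or primary care physician". Section 8.2 places the Early Withdrawal Visit under withdrawal from the study, and 9.1.4 uses it in the same sense.

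**What is wanted of treatment discontinuers.** Sections 5.1 and 8.1 encourage people who permanently stop double-blind treatment to remain and complete the remaining visits. Section 8.1 lists lack of efficacy among the reasons for stopping. Section 10.6.1 makes the primary analysis a de facto one, using every trough FEV1 recorded after randomization.

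**The concern.** The protocol separates stopping treatment from leaving the study, and its primary analysis depends on that separation. The medication rules do not follow it: they end at study completion or at study withdrawal, with nothing at treatment discontinuation.

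The people most exposed are foreseeable. Inclusion criterion 4 admits users of LABA or LAMA. All participants are then on FF 100 mcg without either, and asthma must still be not well controlled at Visit 2. A participant who stops double-blind treatment because it is not working may well need one of the listed controllers.

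Two things are at stake. One is safety: followed exactly, the rule withholds maintenance LABA/LAMA from someone no longer taking the trial drug. The other is retention: leaving the study lifts the bar and staying does not, so the rule may pull against the Week 24 measurement that the de facto analysis needs.

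**Working it through.** **Step 1. When each rule ends**

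| Rule | Section | Ends at |
|---|---|---|
| Table 3 bar | 7.9 | End of study |
| Prior LABA/LAMA stays stopped | 5.1, synopsis | Study completion |
| Own ICS not used | 5.1 | End of run-in and treatment period |
| General release | 7.8 | Early Withdrawal Visit |

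The own-ICS instruction reads: "Participants will refrain from using their own ICS asthma medication during the 2-week run-in and treatment period". It refers to the treatment period, while the LABA/LAMA rule refers to study completion. ICS is not in Table 3, so it is outside this point.

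**Step 2. Whether another section supplies a release**

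- 7.7 requires contact with the sponsor or site monitor when study treatment stops early, but to discuss continued participation. It releases no medicine.
- 7.8 asks for asthma medication in the post-treatment period to be recorded. Recording is not permission.
- 7.8.1.1 has an open-ended list, but for temporary treatment of moderate exacerbations. It does not cover maintenance use.
- Section 9 allows no waivers or exemptions.

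None lifts the bar for a participant who has stopped treatment and stays.

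**Step 3. How long the bar lasts for someone who stops and stays**

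Inputs from the Schedule of Activities: Visit 3 is Day 29, Visit 4 Day 85, Visit 5 Day 169, each with a window of -5/+2 days.

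- Stop at Visit 3: 169 - 29 = 140 days = 20 weeks. With windows, from 164 - 31 = 133 days (19 weeks) to 171 - 24 = 147 days (21 weeks).
- Stop at Visit 4: 169 - 85 = 84 days = 12 weeks. With windows, from 164 - 87 = 77 days (11 weeks) to 171 - 80 = 91 days (13 weeks).

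These are durations under the rule, not effect sizes. The stopping visits are illustrations.

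**Step 4. Sample size, for context**

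Section 10.2 assumes 128 randomized per arm, 10% missing Week 24 spirometry through early withdrawal from the study, a difference of 130 mL, SD 350 mL and two-sided 5%.

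- Evaluable: 128 x 0.90 = 115.2, about 115 per arm.
- Standard error: 350 x sqrt(2/115) = 46.2 mL.
- Power (normal approximation): Phi(130/46.2 - 1.96) = 0.80, as stated.
- Smallest significant difference: 1.96 x 46.2 = 90.5 mL, as stated.

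The plan's figures reproduce and this point does not alter them. As a pure assumption, completers-only power would be 0.782 at 15% missing and 0.757 at 20%, so each further 5 points costs about 2 to 3 points of power. Nothing in the protocol says how much missingness, if any, this rule would add.

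**The case against.** The strongest case against runs as follows.

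- **The retention effect is inferred.** The protocol has no data on it. This stands, so the point says only that the rule may discourage retention.
- **Barred use forces no exit.** The mandatory treatment stops in 8.1 are liver, QTc and pregnancy criteria. A discontinuer could start a LABA as a deviation and stay, and 10.6.1 would use the FEV1 values. Section 8.1 also lets people take part in as much of the study as they are willing or able to. All of this stands. Even so, 8.2 permits withdrawal for compliance reasons, and retention should not rest on deviations.
- **The group is small.** Own ICS is not in Table 3, exacerbations can be treated, and 5.1 has the investigator judge before entry whether LABA/LAMA can be stopped without undue risk. This narrows the group to an unknown size without emptying it.
- **The SRM may cover it.** Section 7.8 refers there for detail and it is not shown. This limits the finding to the protocol text. An SRM release would conflict with 5.1 and 7.9, so the protocol would still need aligning.
- **Holding bronchodilators fixed protects trough FEV1.** That is reasonable while participants are on treatment. Once they have stopped, it fits a de facto question less well.

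A reader might infer that the protocol drives discontinuers out, that the primary comparison is biased, or that the trial is underpowered. The documents support none of these: no exit is required, the direction of any bias is undetermined, and the sample size is sound on its stated inputs.

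**Conclusion.** The point holds as a limited one. In the protocol text, a participant who permanently stops double-blind treatment and stays has no compliant route to maintenance LABA/LAMA or to sustained use of the other Table 3 asthma controllers, while one who withdraws and completes the Early Withdrawal Visit does. This is the consequence of a stated rule, not a detail left for later documents.

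The derivable size is the length of exposure to the rule shown above. The conclusion assumes that at least some participants stop treatment before Week 24 and need such a controller, which the listed stopping reasons make plausible but do not quantify. It is a cheap improvement worth considering, not a flaw that invalidates the analysis.

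**What to change.** **Medication rules (5.1, synopsis, 7.8, 7.9).** State that, from permanent discontinuation of double-blind treatment, the asthma controllers and bronchodilators in Table 3 (LABA, LAMA, anti-leukotrienes, theophyllines and similar) may be prescribed by the investigator or primary care physician and are recorded, whether or not the participant stays. Keep the bar on other investigational drugs, and leave the immunosuppressive row as it is.

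**Spirometry (9.1.3).** Keep the 6-hour rescue withholding and apply it to short-acting anticholinergics. Have the morning dose of any newly started bronchodilator, including theophylline, taken after pre-dose spirometry where clinically possible, and record the time of its last dose. This is needed because the 24-hour rule in 9.1.3 names study treatment only, and the minimum record in 7.8 holds dates, not times.

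**Analysis.** Keep all such FEV1 values in the de facto analysis, including those taken without withholding. The de jure analysis stays.

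**Cost.** A short amendment and one eCRF field, with no extra visits or participants. The downside is that controllers started after stopping may slightly narrow the UMEC-placebo difference, and the previous evening's dose of a twice-daily product may still act at trough. Both are consistent with the de facto estimand.

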7.8.1. Permitted Medications and Non-Drug Therapies

7.8.1.1. Permitted Asthma Medications

In addition to FF 100 mcg and study treatment, the following medications are permitted during this study:

- Study-provided albuterol/salbutamol will be dispensed at Visit 1 for use as relief medication throughout the duration of the study. Participants must be judged capable of withholding albuterol/salbutamol for at least 6 hours prior to study visits.

Temporary changes in medications are permitted for the treatment of moderate asthma exacerbations, at the Investigator's/treating physician's discretion. Asthma exacerbations should be treated in line with national and international recommendations and local medical standards. Asthma medications permitted on a temporary basis to treat a moderate asthma exacerbation include but are not limited to the following (the Medical Monitor may be contacted for additional guidance; see the SRM for contact information [refer to Section 9.1.4.1 for guidance on moderate asthma exacerbation]):

- An increase in ICS dose.
- Systemic corticosteroids (tablets, suspension or injection) for no more than 2 days.
- An Investigator-advised change in SABA use (i.e., routinely scheduled versus as needed use).
- Leukotriene receptor antagonists (LTRAs) and leukotriene modifiers.
- Oral theophylline.

7.8.1.2. Permitted Non-Asthma Medications

The following medications are permitted during this study:

- Medications for rhinitis (e.g., intranasal corticosteroids, antihistamines [including ocular and intranasal], cromolyn, nedocromil, nasal decongestants)
- Note: Use of these medications should be captured on the concomitant medication pages of the eCRF prior to ECG measurements.
- Antibiotics for short term treatment of acute infections. Long term treatment with topical or ophthalmic antibiotics are permitted.
- Decongestants: Participants may take decongestants during the study, but these are disallowed for 24 hours prior to ECG measurements.
- Immunotherapy: Immunotherapy for the treatment of allergies is allowed during the study provided it was initiated 4 weeks prior to Visit 1 and participants remain in the maintenance phase for the duration of the study.
- Topical and ophthalmic corticosteroids.
- Systemic and ophthalmic beta-blockers: Administer with caution as systemic beta-blockers block the pulmonary effect of beta-agonists and may produce severe bronchospasm in patients with reversible obstructive airways disease. Cardioselective beta-blockers should be considered, although they also should be administered with caution.
- Localized corticosteroid injections (e.g. intra-articular and epidural).
- Tricyclic antidepressants and monoamine oxidase inhibitors (MAOIs). (Administer with extreme caution as they may potentiate the effects of beta-agonists on the cardiovascular system, including QTc prolongation)
- Diuretics. (Caution is advised in the co-administration of beta-agonists with non-potassium sparing diuretics as this may result in ECG changes and/or hypokalemia)
- Cytochrome P450 3A4 (CYP3A4) inhibitors (Caution should be exercised when considering the coadministration of long-term ketoconazole and other known strong CYP3A4 inhibitors (e.g., ritonavir, clarithromycin, conivaptan, indinavir, itraconazole, lopinavir, nefazodone, nelfinavir, saquinavir, telithromycin,

troleandomycin, voriconazole) because increased systemic corticosteroid and increased cardiovascular adverse effects may occur)

- Vaccinations (Influenza vaccine, Pneumonia vaccine, Shingles vaccine, etc.) (Administration of influenza and pneumonia vaccines should be considered based on clinical discretion of the Investigator and local/national guidelines. Current influenza vaccines and pneumonia vaccines will be captured on the concomitant medication pages of the eCRF)

All medications for other disorders may be continued throughout the study provided their use would not be expected to affect the participants' lung function or safety assessments (e.g., cardiac measurements). However, no systemic corticosteroids will be permitted.

7.9. Prohibited Medications and Non-Drug Therapies

Use of the medications listed in [Table 3](#) is not permitted during the study.

Table 3 Concomitant Medications

Medication	No use during the study and/or within the following time interval before Visit 1
Inhaled short-acting anticholinergics	6 hours
Inhaled short-acting anticholinergics+ Short-acting beta agonist combination	6 hours
Inhaled long-acting anticholinergics other than study treatment	2 days
Immunosuppressive medications including immunomodulators	12 weeks
Inhaled long-acting beta ₂ -agonists (e.g., salmeterol, formoterol) or combination products containing inhaled long-acting beta ₂ -agonists (e.g., Seretide, Symbicort)	2 days 10 days prior to Visit 1 for Indacaterol and Olodaterol component.
Inhaled very long-acting beta ₂ -agonists, (Indacaterol, Olodaterol) Oral long-acting beta ₂ -agonists (e.g., bambuterol)	
Inhaled short-acting beta ₂ -agonist (rescue albuterol/salbutamol will be provided and is permitted during the study)	6 hours (including all study visits)

Theophyllines, slow-release bronchodilators, ketotifen, nedocromil sodium, sodium cromoglycate, roflumilast	48 hours Temporary use will be permitted during the study to treat moderate asthma exacerbations
Anti-leukotrienes	48 hours. Temporary use will be permitted during the study to treat moderate asthma exacerbations
Any other investigational drug	30 days or within 5 drug half-lives of the investigational drug (whichever is longer)

7.10. Treatment after the End of the Study

Participants will not receive any additional treatment from GSK after completion of the study because other treatment options are available.

The Investigator is responsible for ensuring that consideration has been given to the post-study care of the participant's medical condition, whether or not GSK is providing specific post-study treatment.

8. DISCONTINUATION CRITERIA

8.1. Discontinuation of Study Treatment

Participants that permanently stop study treatment are encouraged to remain in the study. Participants have the right to discontinue study treatment before the end of the study. A participant may also be asked to discontinue study treatment at the Investigator's discretion.

Participants who withdraw from study treatment prematurely (for any reason) should, where possible, continue to be followed-up as per protocol until the completion of the Safety Follow-up assessments. If this is not possible, the Investigator must encourage the participant to participate in as much of the study as they are willing (or able) to.

A participant may be withdrawn from study treatment at any time. A reason for premature discontinuation of study treatment (e.g., AE, lack of efficacy [including moderate or severe asthma exacerbation], protocol deviation, Investigator discretion, consent withdrawn etc.) must be captured in the eCRF.

A participant must be withdrawn from study treatment if any of the following stopping criteria are met:

- Liver Chemistry: Meets any of the protocol-defined liver chemistry stopping criteria
- QTc: Meets any of the protocol-defined stopping criteria
- Pregnancy: Positive pregnancy test

[figure not shown]
